<6.0 mg/dL or an allopurinol dose of 400 mg QD is achieved. The randomization and dosing schema are displayed in Figure 3.a.

Figure 3.a Dose Titration Based on sUA Response and By Baseline Renal Function in the First Three Months of the Study

Serum urate levels will be unblinded to the investigator and Takeda during the first 10 weeks of the study to facilitate dose increases based on sUA response. After the Week 10 Visit, sUA measurements will be blinded to Takeda and the investigator. The interactive voice-activated response system/interactive web-activated response system (IVRS/IWRS) will manage the treatment assignment after randomization and throughout the study medication treatment.

To maintain the double-blind nature of the study, febuxostat and allopurinol tablets will be over-encapsulated and matching placebo capsules will be manufactured which are identical in appearance. Subjects will orally self administer 2 capsules each morning in the appropriate combination for their assigned dose and treatment.

Subjects currently on urate-lowering therapy (ULT) will discontinue treatment at the Day -7 Screening Visit, and will begin colchicine 0.6 mg QD for gout flare prophylaxis. Subjects not on ULT will begin colchicine 0.6 mg QD on the Day 1/Randomization Visit. All subjects will receive gout flare prophylaxis for the first six months of the study medication treatment period. Alternatively, if colchicine is not tolerated and the subject's eCLcr is ≥50 mL/min, they will be administered naproxen 250 mg twice daily with lansoprazole 15 mg QD. If a subject has been

maintained on an appropriate dose (as determined by the investigator) of another proton pump inhibitor other than lansoprazole, he/she may continue treatment with it during this study. In instances when subjects should not receive colchicine or naproxen, other nonsteroidal anti-inflammatory drugs (NSAIDs) or prednisone may be provided at the investigator's discretion.

Following the Day 1/Randomization Visit, subjects will return for study visits during the first 3 months of the study based on the subject's sUA response. Once a subject's sUA <6.0 mg/dL, there will be no further visits until Month 3.

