6.12 Safety Analysis

Safety will be assessed by evaluating the incidence of adverse events including cardiovascular adverse events such as predefined MACE composite, and evaluating ECGs; laboratory tests and vital signs. A CV Endpoints Committee blinded to treatment assignment will adjudicate potential cardiovascular adverse events and each death to determine if it meets MACE criteria. The procedures and rules of adjudication of these events by the CV Endpoints Committee is described in a separate charter.

For the primary, secondary, and additional safety endpoints, time to event will be the time from the date of randomization or the date of last dose of study medication to the date of first occurrence of any event in the respective endpoint. If a subject reports an event for a given safety endpoint after treatment discontinuation, the reported event will be counted toward the treatment to which they were randomized. Subjects who are lost to follow-up during the study or who do not exhibit an episode of an event for the specific safety endpoint throughout the study will be censored at the day of last contact.

All safety endpoints will be analyzed using the Full Analysis Set (FAS). The FAS will consist of all subjects who were randomized and received at least one dose of double-blind study medication. Non-inferiority will be assessed only for the primary safety endpoint.

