6.12.3 Other Safety Endpoints

The following additional safety endpoints will also be assessed:

- The time from randomization to the first occurrence of any event in the pre-defined MACE composite plus any of the following events:

- Urgent Cerebral revascularization [non-elective].
- Hospitalized congestive heart failure (CHF).
- Arrhythmias not associated with ischemia.
- Venous and peripheral arterial thromboembolic events; eg, Deep Vein Thrombosis (DVT) and Pulmonary Embolism (PE).
- Transient Ischemic Attack (TIA).
- The time from randomization to the occurrence of all-cause death,
- The time from randomization to the occurrence of all-cause death during treatment (from randomization to last dose of study medication),
- The time from last dose of study medication to the occurrence of all-cause death,

Survival analysis using the CPH model will be performed for these additional endpoints. Parameter estimates and a 2-sided 95% CI for the hazard ratio will be computed.

Kaplan-Meier plots will also be presented by treatment group.

The following other additional safety analyses will also be performed:

- The number of subjects with first occurrence of predefined MACE that occur no more than 30 days after a subject's last dose of study drug and the associated incidence rate by 100 patient-years of exposure along with 95% confidence intervals will be summarized by treatment group. The 95% CIs will be calculated based on the Poisson distribution. For a given treatment total patient-years (PY) of exposure will be calculated by summing across all subjects the total number of days on the treatment and dividing by 365.

The same analysis will be performed for each component of the MACE composite.

- Mortality analyses for the overall and by CV and Non-CV cause. The total number deaths and the death rate with 95% CI will be presented. The 95% CIs for the death rate will be calculated based on the Binomial distribution using exact method.
- The number and percentage of subjects with first occurrence of a pre-defined MACE composite will be presented by number of days in the study.
- List of CV risk factors for subjects with a predefined MACE composite comprising diabetes, hypertension, hyperlipidemia, obesity, and smoking will be provided by treatment group. Listings include subject number, age, gender, baseline renal function, primary MACE component, disposition, primary reason for discontinuation if disposition is early term, and CV risk factors.

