At the DMC meeting on ^{PPD} [REDACTED], the 75% interim analysis results based on 468 adjudicated MACE for the primary MACE endpoint to assess cardiovascular safety was reviewed by the DMC. At the DMC meeting on ^{PPD} [REDACTED], the DMC informed Takeda that the non-inferiority criterion for the primary endpoint was met at the 75% interim analysis conducted in ^{PPD} [REDACTED]. According to the study design, the study should have been stopped and the non-inferiority of febuxostat relative to allopurinol with regard to cardiovascular risk should have been declared. However the DMC recommendation was to continue the trial without modification until the maximum 624 unique events were achieved to further assess all cause mortality (which was not a protocol specified endpoint) and CV mortality (which is specified only as a component of the MACE endpoint). Takeda agreed to follow the DMC recommendation and continue the study.

Based on the group sequential design, the 75% interim analysis will be the primary analysis for the primary MACE endpoint for the purpose of statistical inference. The continuation of the study to protocol-specified maximum events (624 unique MACE) is for the assessment of all cause mortality and CV mortality. The analyses of all cause mortality and CV mortality with and without death events after discontinuation of treatments will be added to the end of study analysis. An updated sensitivity analysis for the primary MACE endpoint based on 624 unique MACE will also be conducted to provide additional supportive evidence for the primary endpoint.

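### The Cox hazard ratio for death from last dose is taken over the whole FAS, so it blends on-drug with off-drug mortality and misstates the off-drug hazard ratio whenever the two differ

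*SAP*

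**What the plan says.** SAP 4.3 and 6.12.3 list three all-cause mortality endpoints: death from randomisation, death on treatment, and death counted from last dose. The second is "The time from randomization to the occurrence of all-cause death during treatment (from randomization to last dose of study medication". The third is "The time from last dose of study medication to the occurrence of all-cause death". All three get a Cox model with a two-sided 95% CI and Kaplan-Meier plots by arm.

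The rules that apply to them are in SAP 6.12:

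- Population: "All safety endpoints will be analyzed using the Full Analysis Set (FAS"; and "The FAS will consist of all subjects who were randomized and received at least one dose of double-blind study medication".
- Time origin: "time to event will be the time from the date of randomization or the date of last dose of study medication".
- Subjects without the event: "will be censored at the day of last contact".

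SAP 6.1.1 gives only randomisation as the origin for time-to-event endpoints, so it adds no convention for a clock that starts at last dose. On dosing, SAP 3.2 says "Subjects will orally self administer 2 capsules each morning". On purpose, SAP 6.13 says of the period after the 75% look: "The continuation of the study to protocol-specified maximum events (624 unique MACE) is for the assessment of all cause mortality and CV mortality". It then adds analyses of both kinds of mortality with and without deaths after treatment was stopped.

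**The concern.** Everyone in the FAS has taken at least one dose, so everyone has a last dose and enters this analysis. No rule limits it to subjects who stopped drug alive, sets a lag, or says how a time of zero is treated. Someone who dies while taking a daily capsule is then an event at day 0 or 1, with essentially the whole FAS at risk. Someone who completes on drug is censored at about the same point. Only subjects who stopped early contribute follow-up beyond that.

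At stake is whether a mortality difference arises on drug or after withdrawal. SAP 6.13 makes that distinction relevant by asking for mortality with and without off-treatment deaths. As specified, an on-drug difference can appear as one arising after last dose, and a real off-drug difference is diluted.

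There is also a second, separate issue. Subjects with later follow-up are selected by stopping drug, which happens after randomisation. The arms are then no longer protected by randomisation, but the SAP attaches no caveat to the HR.

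**Working it through.** **Plan's own figure.** The SAP gives no event count, rate or power for this endpoint, so there is nothing to reproduce. Its 624 MACE do reproduce (611 events in a fixed design; 90.1% power at 624 with the Table 6.c boundaries) but have no bearing here.

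**Step 1: where each type of subject falls under the written rules.**

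| Subject | Time from last dose | Status |
|---|---|---|
| Dies on drug | about 0-1 day | event |
| On drug at study end | about 0-1 day (assuming last contact is close to last dose) | censored |
| Stopped drug, later dies | days to years | event |
| Stopped drug, alive at last contact | days to years | censored |

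If the last-dose date is imputed as in SAP 6.6, it can equal the date of last contact, giving exactly zero.

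**Step 2: what the HR estimates.** Day 0-1 holds the on-drug deaths, and later days hold almost only off-drug deaths. The partial likelihood splits accordingly, so approximately

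ln HR(reported) = w × ln HR(on) + (1 − w) × ln HR(off),

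where w is the share of events that are on-drug deaths.

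**Step 3: simulation.**

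- From SAP 5.0: 3750 per arm; 2.5 to 5 years of follow-up (2.5 years' accrual, 5 years' maximum participation); and the 10% annual drop-out rate, used as a stand-in for stopping drug.
- Assumed, not in the SAP: stopping at 20%/yr as the alternative; death rates on/off drug of 1%/3%, 2%/4% and 2%/2% per year; the HRs; complete follow-up after stopping; and stopping unrelated to prognosis.
- Method: 200 replicates per setting; unstratified Cox model with Breslow ties.

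Ranges over the six combinations of rates:

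| True HR on/off | Whole FAS, as written | Only those who stopped alive |
|---|---|---|
| 1.0 / 1.5 | 1.08-1.27 | 1.48-1.52 |
| 1.5 / 1.0 | 1.20-1.40 | 0.98-1.01 |
| 1.5 / 0.67 | 1.03-1.34 | 0.65-0.67 |
| 1.2 / 1.2 | 1.19-1.20 | 1.19-1.21 |

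On-drug deaths are about 57-88% of events at 10%/yr stopping and 39-77% at 20%/yr. About 3300-5000 of the 7500 subjects are still on drug at the end and are censored at once.

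**Step 4: formula against simulation.**

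- 10%/yr, 2%/4%, true 1.0/1.5: 450 on-drug and 218 later deaths, w = 450/668 = 0.674. exp(0.326 × 0.405) = 1.14; simulated 1.14.
- 10%/yr, 2%/4%, true 1.5/1.0: 556 and 176 deaths, w = 556/732 = 0.760. exp(0.760 × 0.405) = 1.36; simulated 1.34. The gap arises because the day 0-1 part compares proportions dead, not rates. That ratio is about (556 − 225)/225 = 1.47, taking half of 450 as the control deaths, and exp(0.760 × 0.386) = 1.34.
- 20%/yr, 1%/3%, true 1.5/0.67: 239 and 203 deaths, w = 239/442 = 0.541. exp(0.541 × 0.405 − 0.459 × 0.400) = 1.04; simulated 1.03.

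**Step 5: can the two truths be told apart?** At 20%/yr and 1%/3%, true 1.0/1.5 gives 1.27 and true 1.5/1.0 gives 1.20. The log difference of about 0.06 is smaller than either log-HR standard error (about 0.09). At 10%/yr and 2%/4% the results are further apart (1.14 and 1.34), but neither is near the true off-drug HR.

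**The case against.** The strongest reply is that the SAP nowhere says on-drug deaths count here. The endpoint follows directly after the during-treatment one, so the pair may be meant to split follow-up at last dose. That is a fair reading of intent, but it removes only deaths on the last-dose date. The companion endpoint stops exactly at last dose, so a death on the next morning, before the next capsule, is outside it and falls into this one.

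A reader might also infer one of three stronger conclusions:

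- *That the endpoint cannot show anything about risk after stopping.* The documents do not support this. The blend affects the single Cox HR, and only when on- and off-drug HRs differ (1.2/1.2 gives about 1.2). The planned Kaplan-Meier plot would show a step at day 0-1 and could be read conditionally beyond it, though no such analysis is specified.
- *That the mortality assessment for which the trial continued is compromised.* It is not. Death from randomisation is untouched, and SAP 6.13 separately plans mortality with and without off-treatment deaths. SAP 6.12 confines non-inferiority testing to the primary endpoint.
- *That the remedy must drop the first 30 days or return to time since randomisation.* These are choices of estimand. Excluding 30 days discards the period in which a withdrawal effect could appear, and time since last dose is a defensible scale for that question.

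It is also true that the sizes rest on assumed rates, and that a simulation in which stopping is unrelated to prognosis does not test the selection problem. It shows only that restriction removes the blending.

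**Conclusion.** The point holds for the Cox HR from last dose. The whole-FAS population, last-dose origin and censoring at last contact are stated rules. With daily dosing they put on-drug deaths at day 0-1, and the resulting HR misstates the off-drug effect whenever it differs from the on-drug effect. The structure does not depend on the assumed rates; the size does. Over the rates tried, on-drug deaths are roughly 40-90% of events, and an off-drug HR of 1.5 (with 1.0 on drug) is reported as about 1.1-1.3. An off-drug HR of 1.0 (with 1.5 on drug) is reported as about 1.2-1.4. An off-drug HR of 0.67 with 1.5 on drug comes out above 1, in the wrong direction.

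Importance is moderate: this is an additional endpoint without a formal test, and the main mortality analysis stands. It is still worth correcting, because the SAP asks for mortality on and off treatment to be distinguished.

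**What to change.** In SAP 4.3 and 6.12.3:

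1. Limit the endpoint to subjects who permanently discontinued study drug alive and have follow-up after stopping.
2. Assign deaths on drug (day 0-1 after last dose, with no prior discontinuation) to the during-treatment endpoint, and state how a time of zero is handled.
3. Keep time since last dose as the time scale and stratify the Cox model by baseline renal function.
4. Label the HR a descriptive, non-randomised comparison, because stopping drug happens after randomisation.
5. Tabulate deaths and person-years by arm for three periods: on drug, within 30 days of stopping, and later. Exclude the first 30 days only as a sensitivity analysis; SAP 6.12.1, 6.12.3 and 6.12.4 already use that window. The table also shows deaths a few days after the last capsule, where a final illness may itself have ended dosing.

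The cost is SAP wording and minor programming on dates already collected. The real downside is precision: under the assumed rates the log-HR standard error rises from about 0.07-0.10 to 0.10-0.24. The 95% limits then lie a factor of about 1.22 to 1.60 either side of the estimate (exp(1.96 × 0.10) and exp(1.96 × 0.24)), against about 1.15 to 1.22 now.

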5.0 DETERMINATION OF SAMPLE SIZE

A total of 7500 subjects (3750 per treatment group) are planned to be enrolled in this study. The sample size will provide at least 90% power to meet a non-inferiority margin of 1.3 for the hazard ratio (febuxostat relative to allopurinol) of the primary endpoint. The sample size calculation assumed a true hazard ratio of 1.0 at a 1-sided 2.5% significance level with 3 interim analyses at approximately 25%, 50% and 75% of the events based on critical values obtained using the Lan-DeMets - O'Brien-Fleming alpha spending function.

For the determination of non-inferiority between the febuxostat treatment group and the allopurinol treatment group, the sample size calculation further assumed:

- Constant proportional hazards and exponential survival curves,
- Annual adjudicated MACE composite rate of 2.8%,
- Maximum length of participation of 5 years,
- Accrual time of 2.5 years, and
- Annual drop-out rate of 10%.

This study is designed to have a maximum of 624 MACE.

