6.12.2 Secondary Safety Endpoints

The following secondary safety endpoints will be assessed:

- The time from randomization to the first occurrence of any Antiplatelet Trialists' Collaborative (APTC) event (CV Death, Non-fatal MI, and Non-fatal Stroke).
- The time from randomization to the occurrence of each individual event in the pre-defined MACE composite.

Survival analysis using the CPH model will be performed on the time to the first occurrence of any APTC event and on the time to occurrence of each individual event in the pre-defined MACE composite. Parameter estimates and 2-sided 95% CIs for the hazard ratio will be computed. A graphical display indicating the point and 95% CI estimates of the hazard ratios for the primary MACE components will also be presented.

To identify risk factors for the time to first occurrence of APTC event, an exploratory analysis will also be performed using multivariate CPH modeling. The multivariate model will include treatment group and the following covariates jointly in the model with baseline renal function as the stratification factor: age, gender, BMI, NSAIDs use, low-dose aspirin use, smoking history, baseline sUA, and history of diabetes, hypertension, non-fatal MI, or non-fatal stroke. No interaction terms will be introduced in the multivariate model. The backward elimination technique with a significance level to stay (SLS) in the model of SLS = 0.05 will be implemented for variable selection while always retaining treatment group and baseline renal function as stratification factor in the model.

In addition, Kaplan-Meier plots for the time to first occurrence of APTC event and the time to first occurrence of each individual event in the pre-defined MACE will be presented by treatment group.

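### Overall, CV and non-CV death rates are planned as crude binomial proportions despite variable follow-up, which understates absolute mortality (minor)

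*SAP*

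**What the plan says.** Section 6.12.3 lists mortality analyses overall and by CV and non-CV cause. The content is brief: "The total number deaths and the death rate with 95% CI will be presented", and then "The 95% CIs for the death rate will be calculated based on the Binomial distribution using exact method". The bullet gives no denominator; under 6.12 it would presumably be the Full Analysis Set. It plans no ratio, difference or test between arms.

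The same section covers time to all-cause death (overall, on treatment, and after the last dose): "Survival analysis using the CPH model will be performed for these additional endpoints", with hazard ratios, 95% intervals and Kaplan-Meier plots. Section 6.12.2 fits a Cox model "on the time to occurrence of each individual event in the pre-defined MACE composite. Parameter estimates and 2-sided 95% CIs for the hazard ratio", and CV death is one of those components. In these analyses, section 6.12 says that subjects lost to follow-up or without the event "will be censored at the day of last contact".

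The bullet just before the mortality one gives MACE and each component per 100 patient-years of exposure with Poisson intervals, for events up to 30 days after the last dose.

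Section 3.2 says participation varies because the study is event driven. Section 5.0 assumes "Annual drop-out rate of 10" per cent. Section 6.13 says of the decision to go on after the 75% interim analysis: "The continuation of the study to protocol-specified maximum events (624 unique MACE) is for the assessment of all cause mortality and CV mortality". It names no method for the mortality analyses it adds.

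**The concern.** Deaths divided by subjects estimates a mortality risk only when everyone has been observed over the same period. In this trial a subject lost at Month 2 stays in the denominator as if alive to the end. The proportion therefore depends on how long people were followed as well as on how often they died, and it refers to no particular time point.

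The absolute death rates are the figures most likely to be lifted from the report, and the trial was continued "to further assess all cause mortality" and CV mortality. Non-CV death has no Cox model, Kaplan-Meier plot or person-time rate listed, so the crude proportion is all a reader would have for it.

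**Working it through.** **Inputs from section 5.0:** 7500 subjects (3750 per arm), accrual 2.5 years, maximum participation 5 years, MACE 2.8% per year, drop-out 10% per year, exponential curves. **Assumed, not in the SAP:** uniform accrual; constant mortality of 1.5 to 2.5% per year; a subject who drops out has no later death recorded.

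**Formula.** With event hazard λ, drop-out hazard η and k = λ + η, and potential follow-up uniform from 2.5 to 5 years:

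- A = (e^(−2.5k) − e^(−5k)) / (2.5k)
- expected crude proportion p = (λ/k)(1 − A)
- expected follow-up per subject = (1 − A)/k years

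**Check against the plan's own figure.** Take λ = −ln(0.972) = 0.0284 and η = −ln(0.90) = 0.1054. Then p = 0.08315, and 7500 × 0.08315 = 624 MACE, the planned maximum. This supports reading 10% as an annual probability.

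**Shortfall with the same drop-out in both arms.**

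| Assumed mortality | p, no drop-out | p, 10% per year | Ratio |
|---|---|---|---|
| 1.5% | 5.46% | 4.50% | 0.82 |
| 2.5% | 8.93% | 7.36% | 0.82 |

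For the last row, k = 0.1304, A = 0.616 and p = (0.025/0.1304) × 0.384 = 0.0736. The crude figure is about 18% too low in relative terms. Treating 10% as a hazard instead (η = 0.10) gives 7.43% and 4.54%, a shortfall of 17%.

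**What the interval covers.** At 2.5% mortality one arm expects 0.0736 × 3750 = 276 deaths. The exact binomial interval for 276/3750, from the 2.5% point of Beta(276, 3475) and the 97.5% point of Beta(277, 3474), is 6.54% to 8.24%. It excludes 8.93%.

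**Person-time on the same data.** Expected follow-up is 0.384/0.1304 = 2.945 years per subject, or 11,045 patient-years per arm. The rate is 276/11,045 = 2.50 per 100 patient-years (exact Poisson 2.21 to 2.81), which recovers the assumed mortality.

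**Across arms at equal mortality of 2.5%** (the arm differences are assumed; the SAP gives one drop-out rate):

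| Drop-out per year | Crude proportions | Crude ratio | Rate ratio |
|---|---|---|---|
| 10% v 10% | 7.36% v 7.36% | 1.00 | 1.00 |
| 12% v 10% | 7.08% v 7.36% | 0.96 | 1.00 |
| 15% v 10% | 6.67% v 7.36% | 0.91 | 1.00 |

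At 1.5% mortality the crude ratios are the same to two decimals.

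**The case against.** The strongest reply is that the binomial figure is only a descriptive line. All-cause and CV death are compared by Cox models with censoring at last contact and Kaplan-Meier plots. CV death also gets an on-treatment patient-year rate as a MACE component. All of that stands. Because section 6.13 makes mortality the reason for continuing, a reader might infer that the binomial rule distorts that comparison. The documents do not support this: 6.13 does not name the binomial rate as its method, and no between-arm test uses it.

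The interval is also not miscalculated. If follow-up times come from one distribution, deaths out of N are binomial and the exact interval is valid for the chance that a death is recorded. That stands too, but that chance is not a mortality risk, and the plan calls it a death rate.

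With equal drop-out the contrast between arms is nearly intact: a true hazard ratio of 1.2 gives a crude ratio of 1.19. Distortion between arms needs a drop-out difference that the SAP does not state.

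A reader might also carry the calculation to the 9-year study length in section 3.2 and find larger effects. Pairing 9 years with 2.5-year accrual gives 6.5 to 9 years of potential follow-up, and the formula then yields about 1,025 MACE against the maximum of 624. Those inputs do not fit together.

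The contrast with the MACE bullet is only a partial inconsistency, because that summary is restricted to on-treatment events. Finally, section 3.2 follows subjects off study drug by phone unless they withdraw consent. If part of the 10% is still followed for death, the shortfall is smaller.

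**Conclusion.** The point holds as a minor one about absolute mortality. As specified, the overall, CV and non-CV death rates are crude proportions that count subjects lost early as survivors. They understate mortality by about 18% relative to no drop-out under the section 5.0 design. That size assumes constant hazards, 10% annual loss that ends ascertainment of death, and mortality of 1.5 to 2.5% per year; it barely changes across that mortality range. Any effect on the reading across arms is conditional on unequal drop-out: a ratio of 0.96 for an assumed 12% against 10%. The hazard ratios and Kaplan-Meier plots for all-cause and CV death are untouched. Non-CV death is the most exposed, because no other estimate is listed for it.

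**What to change.** In 6.12.3, report overall, CV and non-CV deaths per 100 patient-years of follow-up, from randomisation to death or last contact, with exact Poisson intervals. Add cumulative incidence estimates for CV and non-CV death, each treating the other as a competing event. If the binomial figure is kept, label it a crude proportion of subjects and state its denominator.

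One detail needs wording. For a subject with a MACE after stopping treatment, section 6.6 sets last contact at the MACE start date. The follow-up time used for deaths should run to the death or to the true last contact, so that no death falls outside its own person-time.

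The cost is a sentence or two and one extra table. Section 6.6 already derives participation from randomisation to last contact, so no new data are needed.
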